8.4.2 Safety Analysis Endpoints

Refer to Section 4.2.3.2 for the description of the safety measures in this trial.

Safety and tolerability will be assessed by clinical review of all relevant parameters including AEs. Tier 1 events for this trial consist of the solicited injection-site and solicited systemic AEs.

8.5 Analysis Populations

8.5.1 Immunogenicity Analysis Populations

The Per-Protocol (PP) population will serve as the primary population for the analysis of immunogenicity data in this trial. The PP population consists of those subjects who are not considered as protocol violators. Violations include but are not limited to: failure to receive the scheduled doses [at least 28 days between doses 1 and 2 and between doses 2 and 3 (for PD3, Pre-dose 4, and PD4 PP analyses), and dose 4 at 12 months to 15 months of age (for PD4 PP analyses)] of correct clinical material, and lack of valid serology results available from 28 to 42 days following the dose being analyzed. The final determination on protocol violations will be made prior to unblinding of the database and will be documented in a separate memo.

The Full Analysis Set (FAS) population will also be used for supplementary analysis of the primary analyses. The FAS population consists of all randomized subjects who received at least one vaccination and have at least one serology result. Subjects will be included in the vaccination group to which they are randomized for the analysis of immunogenicity data.

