- d. In order to avoid bias, the unblinded trial personnel will have no further contact with trial subjects for any trial-related procedures/assessments following administration of the trial vaccines. This includes all safety follow-up procedures. Contact between subjects and unblinded trial personnel after vaccination administration is strictly prohibited. The study vaccine should be removed from the refrigerator no more than 1 hour before vaccination and time of removal and time of vaccination should be noted in subject's chart.
- e. Concomitant (or routine pediatric) vaccines are to be given according to recommended schedule. Any injectable concomitant vaccines provided at the visit must be given after the trial vaccine and in a separate limb, may be given during the 30-minute observation period, and do not require additional observation time. Concomitant oral vaccines may be administered prior to the trial vaccine and other injectable concomitant vaccine.
- f. Adverse events (serious and non-serious) are to be reported from Day 1 to 14 days following each vaccination. Serious Adverse events are to be reported from treatment/randomization through 30 days following the last study vaccination.
- g. Pre-vaccination temperatures taken by trial staff at Visits 1, 2, 3 and 5. Subjects who have febrile illness (rectal temperature $\geq 38.1^{\circ}\text{C}$ [$\geq 100.5^{\circ}\text{F}$] or axillary temperature $\geq 37.8^{\circ}\text{C}$ [$\geq 100.0^{\circ}\text{F}$]) occurring at or within 72 hours of Visits 1, 2, 3 and 5 must be rescheduled. Parent/legal guardian to measure and record temperature per VRC instructions.
- h. Leftover serum samples collected from the main trial will be stored for future use if the FBR consent is signed.
- i. Collect blood prior to vaccination.
- j. Day of first trial vaccination = Day 1 of trial. To calculate visit windows for subsequent trial vaccinations, confirm subject DOB and ensure the age of the subject will fall within the appropriate age range for each trial visit.
- k. Start and stop time for the 30 minute post vaccination observation period must be noted in subject chart.
- l. Subjects who discontinue the study early may be asked to return for a post-trial visit, see Section 7.1.5.3 for details.
- m. Record prior medications taken by the subject within 30 days before first vaccination.

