7.1.3.2 Blood Collection for Immunogenicity Assays

Subjects will have blood drawn (approximately 4-5 mL) at 3 time points: (1) approximately 1 month following the third study vaccination (PD3), (2) immediately prior to administration of the fourth study vaccination, and (3) approximately 1 month following the fourth study vaccination (PD4). Sera will be used to measure vaccine-induced pneumococcal-specific immune responses (IgG and opsonophagocytic killing activity [OPA]). These serum samples will be assayed using the Meso-Scale Discovery MSD Pn ECL assay, which was developed by Merck & Co., Inc. for the measurement of pneumococcal capsular polysaccharide IgG antibodies. Serum samples will also be assayed using a 4-Fold Multiplex Opsonophagocytic Assay which Merck has developed and implemented in collaboration with [REDACTED]

[REDACTED]^{PPD}. If a serum sample does not have enough volume for both the IgG and OPA testing, the IgG testing will take priority. OPA will be evaluated in approximately 50% of subjects enrolled at US investigator sites with sufficient PD3 sera available to perform both the PnECL and the OPA testing on all 15 serotypes in V114. OPAs will be conducted at pre-dose 4 and at PD4 for all of the subjects who had PD3 OPAs performed and for which there is sufficient serum. Any remaining sera will be retained for future biomedical research (e.g., pneumococcal assay development) providing the future biomedical research (FBR) consent has been signed.

Pneumococcal Electrochemiluminescence (Pn ECL) Assay

The purpose of the Pn ECL assay is to detect serum IgG antibody to the pneumococcal polysaccharides (PnPs) serotypes 1, 3, 4, 5, 6A, 6B, 7F, 9V, 14, 18C, 19F, 19A, 22F, 23F, and 33F before and after vaccination with PnPs containing vaccine(s). The serotypes are assayed in a group of 7 (types 1, 5, 6A, 7F, 19A, 22F, 33F) and a group of 8 (types 3, 4, 6B, 9V, 14, 18C, 19F, 23F). Antibodies to these serotypes are measured in mass units (μ g/mL) read from a standard curve prepared from a pool of adult serum, collected postvaccination with a PPV23 and referred to as 007sp.

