8.0 STATISTICAL ANALYSIS PLAN

This section outlines the statistical analysis strategy and procedures for the study. Changes to analyses made after the protocol has been finalized, but prior to unblinding, will be documented in a supplemental SAP (sSAP) and referenced in the Clinical Study Report (CSR) for the study. Post hoc exploratory analyses will be clearly identified in the CSR.

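### Does the 28 to 42 day serology rule shut pre-dose 4 samples out of the per-protocol analysis?

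*Combined protocol and SAP*

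**What the plan says.** Section 8.5.1 defines the per-protocol (PP) population as the subjects who are not considered protocol violators. It introduces its examples with "Violations include but are not limited to".

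- **Dosing conditions.** These are tagged by analysis. The minimum intervals between doses 1 and 2 and "between doses 2 and 3 (for PD3, Pre-dose 4, and PD4 PP analyses") cover all three time points, and the dose 4 age condition is limited to PD4.
- **Serology condition.** This is "lack of valid serology results available from 28 to 42 days following the dose being analyzed", with no tag.
- **Final decision on violations.** This "will be made prior to unblinding of the database and will be documented in a separate memo".

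The pre-dose 4 sample is taken at Visit 5. Footnote i of the flow chart (Section 6.0) reads "Collect blood prior to vaccination", and Section 7.1.3.2 places the draw "immediately prior to administration of the fourth study vaccination".

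Table 3 lists PP as the only population for the secondary pre-dose 4 GMCs. The Full Analysis Set "will also be used for supplementary analysis of the primary analyses", so it has no stated role at pre-dose 4. Section 8.0 adds that changes to analyses made after the protocol is final but "prior to unblinding, will be documented in a supplemental SAP (sSAP").

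**The concern.** The sentence tags its dosing conditions by time point and names a pre-dose 4 PP analysis, then leaves the serology condition untagged. Taken at its word, the condition applies at pre-dose 4 as well, where no sample drawn on schedule can satisfy it.

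If the dose under analysis is instead taken to be dose 3, the rule tests a different bleed. An infant with a valid Visit 5 result would be left out because the Visit 4 bleed was late or missing. Two programmers could follow the text and build different pre-dose 4 populations.

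At stake are the secondary pre-dose 4 IgG GMCs and GMC ratios, for which PP is the only listed population, and the exploratory pre-dose 4 response rates and OPA summaries.

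**Working it through.** No sample size, power or alpha figure in the plan depends on this clause, so there is no stated figure to reproduce. The check is a day count, a comparison of readings, and an illustration of precision.

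**Inputs (Sections 5.2.2 and 6.0).**
- Dose 3: 6 months of age to 1 day before 7 months.
- Visit 5 (bleed, then dose 4): 12 months of age to 1 day before 16 months.
- Visit 4: 28 to 42 days after dose 3.
- Visit 6: 28 to 42 days after dose 4.

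**Day count from dose 3 to the pre-dose 4 bleed.**
- Shortest: 12 months − (7 months − 1 day) = 5 months + 1 day. The shortest five-month span is 1 February to 1 July in a non-leap year: 28 + 31 + 30 + 31 + 30 = 150 days. So 150 + 1 = 151 days.
- Longest: (16 months − 1 day) − 6 months = 10 months − 1 day. The longest ten-month span, such as 1 March to 1 January, is 306 days. So 306 − 1 = 305 days.
- Past the 42-day limit: 151 − 42 = 109 days at least, and 305 − 42 = 263 days at most.

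Enumerating birth dates from 2015 to 2022 under two month-end conventions gives the same limits. Measured from dose 4, the sample precedes the dose. The literal observation is therefore correct: no in-window pre-dose 4 sample falls 28 to 42 days after any dose.

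**Three readings of the clause.**

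| Reading | Effect at pre-dose 4 |
|---|---|
| Every sample, at every time point, must fall 28 to 42 days after a dose | No sample qualifies |
| The clause covers PD3 and PD4 only | No infant is lost; a valid Visit 5 result suffices |
| Dose 3 is the reference, judged by subject | Infants without a valid Visit 4 result in window are left out |

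The first reading conflicts with the rest of the sentence, which plans a pre-dose 4 PP analysis. It also treats a definition of subjects as a test of single samples. The second fits the schedule: Visits 4 and 6 are the only two visits with a 28 to 42 day window. The third is workable and has a partial parallel in Section 4.2.3.1, where OPA is run at pre-dose 4 only for infants who had it at PD3.

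**Precision under the third reading (illustration).** The documents give no share of infants with a late or missing Visit 4 bleed but a valid Visit 5 sample. Assume the same share p is lost from each arm. Intervals for log GMCs and log GMC ratios then widen by about 1/√(1 − p). With 350 infants per arm at Visit 5:

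| p (assumed) | Infants lost per 350 | Width factor |
|---|---|---|
| 0.02 | 7 | 1/√0.98 = 1.010 |
| 0.05 | 17.5 | 1/√0.95 = 1.026 |
| 0.10 | 35 | 1/√0.90 = 1.054 |

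**The case for a change.** The strongest case for changing the text has four parts.

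1. **An open-ended list can add violations but does not cancel one already listed.** This is true. But the memo need not cancel anything. It only has to say which dose is under analysis at each time point, and Section 8.5.1 reserves the final determination of violations to it.
2. **Nothing in the documents shows the point settled, and no supportive population is specified for pre-dose 4.** This stands as a description of the text. The supplemental SAP is not among the documents, so it cannot be said whether it closes the gap.
3. **The memo need only precede database unblinding, whereas the trial team sees group-level PD3 IgG summaries at the interim (Section 8.7).** This is a fair remark on timing. However, the interim endpoints in Table 5 are all PD3, so those summaries contain no pre-dose 4 results to steer the choice.
4. **One tagged phrase would remove the doubt at almost no cost.** The cost is indeed small, but the wording is not quite neutral. PD3 serology drives the rescue rule in Section 5.6, under which infants who meet it leave the trial. A pre-dose 4 set that needs only a Visit 5 result would mix infants assessed against that rule with any who had no Visit 4 result. Whether to require a PD3 result is a choice the sponsor can reasonably make either way.

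What survives is narrow: the clause lacks a time-point tag, and the pre-dose 4 sample has no serology criterion of its own in the visible text.

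**Conclusion.** The day count is right, but it counts only against a reading that an analyst would not use. On the probable intent the loss is zero. On the dose 3 reading the condition is defensible. Its precision cost cannot be determined from the documents; it is about 1.0% to 5.4% wider intervals under assumed equal losses of 2% to 10% per arm.

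The affected secondary objective (Section 3.2) is estimation without a hypothesis, and the remaining pre-dose 4 endpoints are exploratory. The primary PD3 comparison, its power and the type I error control do not use this sample, and the documents give no reason to expect a difference between arms in who would be left out.

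This is a gap in detail that analysts would fill sensibly in the memo before unblinding or in the supplemental SAP, so no change to the plan is called for. The conclusion assumes that the pre-dose 4 population is fixed there without sight of results by arm at that time point. A sponsor already editing Section 8.5.1 could tag the clause for clarity, but nothing in the analysis depends on it.

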8.5.2 Safety Analysis Populations

The ASaT population will be used for the analysis of safety data in this trial. The ASaT population consists of all randomized subjects who received trial vaccine. Subjects will be included in the group corresponding to the clinical material they actually received for the analysis of safety data using the ASaT population. For most subjects this will be the group to which they are randomized. Subjects who receive incorrect clinical material will be included in the group corresponding to the clinical material actually received.

8.6 Statistical Methods

For immunogenicity analyses, unless otherwise specified, all statistical tests will be conducted at the $\alpha=0.05$ (two-sided) level. Results that will be considered to be statistically significant (versus nominally significant) after consideration of the strategy for controlling type-I errors, are described in Section 8.8, Multiplicity.

8.6.1 Statistical Methods for Immunogenicity Analyses

The immunogenicity analyses will be conducted for each serotype separately.

For the primary hypothesis, a V114 lot will be considered non-inferior to Prevnar 13™ if the lower bound of the two-sided 95% confidence interval (CI) for the between-treatment difference (V114 - Prevnar 13™) in the proportion of subjects meeting serotype-specific IgG $\geq 0.35 \mu\text{g/mL}$ at 1 month post-dose 3 for the 13 serotypes (1, 3, 4, 5, 6A, 6B, 7F, 9V, 14, 18C, 19F, 19A and 23F) in common between V114 and Prevnar 13™ is >-0.15 (15 percentage point non-inferiority margin). The proposed 15 percentage point provides adequate precision around the primary immunologic endpoints and greater confidence in predicting the outcome of the Phase III pivotal study. The Miettinen and Nurminen approach will be used.

The within-group IgG GMC along with two-sided 95% CIs will be computed for all 15 serotypes included in V114. Point estimates of GMCs are the exponentiated estimates of the mean natural log concentrations. The confidence limits for GMCs are the exponentiated confidence limits for the mean natural log concentrations, based on 1-sample t-distributions. Additionally, GMC ratios (V114/Prevnar 13™) along with two-sided 95% CIs will be computed for each of the two V114 lots (V114-1 and V114-2) relative to Prevnar 13™ for all 15 serotypes included in V114. The 95% CI for the ratio will be calculated using the t-distribution with the variance estimate derived from a linear model utilizing the log-transformed antibody titers as the response and a single term for vaccination group (including the subjects from both V114 lots and Prevnar 13™).

A detailed analysis strategy for immunogenicity endpoints is listed in [Table 3](#).

Table 3 Analysis Strategy for Immunogenicity Variables

Endpoint/Variable (Description, Time Point)	Statistical Method	Analysis Population	Missing Data Approach
Primary Objectives			
Proportion of subjects with PD3 IgG $\geq 0.35 \mu\text{g/mL}$ for the 13 common serotypes between V114 and Prevnar 13™	Non-inferiority of V114 compared with Prevnar 13™, based on difference in percentages (Miettinen and Nurminen)	PP [Primary] FAS [Supportive]	Missing data will not be imputed
The PD3 IgG GMCs for all 15 serotypes included in V114	
 Within-group GMCs and 95% CI GMC ratio (V114/Prevnar 13™) and 95% CI (t-distribution with the variance estimate from a linear model including the subjects from both V114 lots and Prevnar 13™) 	PP [Primary] FAS [Supportive]	Missing data will not be imputed
Secondary Objectives			
The pre-dose 4 and PD4 IgG GMCs for all 15 serotypes included in V114	
 Within-group GMCs and 95% CI GMC ratio (V114/Prevnar 13™) and 95% CI (t-distribution with the variance estimate from a linear model including the subjects from both V114 lots and Prevnar 13™) 	PP	Missing data will not be imputed
GMC = Geometric Mean Concentration GMFR = Geometric mean fold rise from Day 1. PP = Per-protocol FAS = Full Analysis Set CI = Confidence interval			

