3.0 OBJECTIVE(S) & HYPOTHESIS(ES)

3.1 Primary Objective(s) & Hypothesis(es)

In healthy infants receiving one of the 2 V114 lots or Prevnar 13™ at approximately 2, 4, 6, and 12-15 months of age:

1. **Objective:** To describe the safety and tolerability profiles of 2 different lots of V114 [Lot 1 (V114-1), Lot 2 (V114-2)], after each dose.

2. **Objective:** To demonstrate that V114 (either V114-1 or V114-2) is non-inferior to Prevnar 13TM for the 13 shared serotypes (1, 3, 4, 5, 6A, 6B, 7F, 9V, 14, 18C, 19A, 19F, and 23F), based on the proportion of subjects meeting serotype-specific immunoglobulin G (IgG) threshold value of ≥ 0.35 $\mu\text{g/mL}$ at 1 month post-dose 3 (PD3).

Hypothesis: The proportion of subjects receiving V114 (either V114-1 or V114-2) who have serotype specific IgG ≥ 0.35 $\mu\text{g/mL}$, as measured by the Pn ECL assay, for each of pneumococcal serotypes 1, 3, 4, 5, 6A, 6B, 7F, 9V, 14, 18C, 19A, 19F, and 23F at 1 month PD3 is non-inferior to that for recipients of Prevnar 13TM.

[The statistical criterion for non-inferiority corresponds to the lower bound of the adjusted 95% CI of the proportion difference (V114 minus Prevnar 13TM) being greater than -0.15 for each of the 13 shared serotypes.]

3. **Objective:** To evaluate the serotype-specific IgG geometric mean concentrations (GMCs) of V114-1, V114-2, and Prevnar 13TM, and the IgG GMC ratios between each of the two V114 lots and Prevnar 13TM for all 15 serotypes included in V114 (1, 3, 4, 5, 6A, 6B, 7F, 9V, 14, 18C, 19A, 19F, 22F, 23F, and 33F) at 1 month PD3.

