4.1.4 Information on Other Trial-Related Therapy

In this trial, Prevnar 13TM will be administered as one of the trial vaccines, to serve as the active comparator. In addition to the administration of trial vaccine (V114 or Prevnar 13TM), other pediatric vaccines will be administered concomitantly according to the recommended schedule for sites in the United States and according to local, regional, and/or country guidelines outside of the United States.

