5.4 Stratification

No stratification based on age, sex or other characteristics will be used in this trial.

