7.1.1.8.2 Concomitant Vaccinations

No other investigational compound or device may be administered at any time during this study without prior approval by the SPONSOR.

¹ Needles provided in Prevnar 13TM blister packages may also be used.

² Per investigator discretion, dose 4 can be administered in the deltoid muscle instead of the anterolateral thigh muscle; if given in the deltoid muscle, the needle length should be 5/8 to 1 inch (a 5/8 inch needle may be used only if the skin is stretched tight, subcutaneous tissue is not bunched, and injection is made at a 90-degree angle).

The study vaccines will be administered at approximately 2, 4, 6, and 12 to 15 months of age. Other pediatric vaccines will be administered concomitantly according to the mandated schedule in the site's country/region. These concomitant non-study vaccinations will be recorded on the appropriate eCRF. Combination MMRV vaccines should not be given in this study; however, MMR and Varicella vaccines are permitted if administered concomitantly in 2 separate limbs.

Concomitant vaccines (oral or injectable) should be administered on the same day as study vaccine. Concomitant oral vaccines may be administered prior to the study vaccine and other injectable concomitant vaccines. Precautions must be taken to prevent choking during the administration of oral vaccines. Concomitant injectable vaccines should be administered after the study vaccine. To avoid any confounding results, non-study injectable vaccines should not be administered in the same limb as study vaccine. Documentation of which limb was used for the administration of study vaccine should be recorded on the appropriate eCRF. As we are requesting the reporting of injection-site adverse experiences from the study vaccine (and not from the concomitant vaccines), this information should also be recorded on the VRC to inform the parent/legal guardian of the appropriate limb to monitor for adverse experiences ONLY related to the study vaccine.

During the influenza season, it is anticipated that trial subjects 6 months of age and older may be given an influenza vaccine. Influenza vaccine should be administered either 14 days prior to or 30 days after the administration of the trial vaccine.

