8.10 Subgroup Analyses and Effect of Baseline Factors

The GMC responses as measured by Pn ECL to all 15 serotypes contained in V114 will be summarized by vaccination group in each country subgroup, in order to assess potential differences by this factor.

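### The GMC-ratio model is valid with vaccination group as its only term, but adding country as a pre-specified covariate might give slightly tighter intervals at little cost

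*Combined protocol and SAP*

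**What the plan says.** - **Model.** Section 8.6.1 states: "The 95% CI for the ratio will be calculated using the t-distribution". The variance comes from a linear model fitted to all three arms, "utilizing the log-transformed antibody titers as the response and a single term for vaccination group". Table 3 repeats the linear model for PD3, pre-dose 4 and PD4 and names no covariate.
- **Status of the endpoint.** Primary objective 3 in Section 3.1 is an estimation objective: "To evaluate the serotype-specific IgG geometric mean concentrations (GMCs" and their ratios to Prevnar 13 at PD3. It has no hypothesis or margin. The secondary objective in Section 3.2 does the same at pre-dose 4 and PD4.
- **Country in the analysis.** Under Section 8.10, GMCs "will be summarized by vaccination group in each country subgroup, in order to assess potential differences by this factor". No other subgroup factor is listed.
- **Country in conduct.** Section 4.1.4 says that other childhood vaccines are given on the recommended schedule at United States sites and "according to local, regional, and/or country guidelines outside of the United States". Section 7.1.1.8.2 agrees: "Other pediatric vaccines will be administered concomitantly according to the mandated schedule in the" site's country or region.
- **Randomisation.** Section 5.4: "No stratification based on age, sex or other characteristics will be used in this trial".
- **Sampling.** Section 4.2.3.1 lists three blood draws, at PD3, pre-dose 4 and PD4. There is no serum from before dose 1, so a baseline IgG covariate does not exist.

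**The concern.** The plan treats country as a factor worth examining for GMCs, and it lets country determine which other vaccines are given on the same day. Neither the randomisation nor the model takes account of it. Any between-country variation in log IgG therefore stays in the residual and widens every GMC-ratio interval. With no pre-vaccination sample, country is one of the few baseline factors that could reduce that residual.

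What is at stake is the precision of 15 serotypes x 2 lots x 3 time points = 90 ratios. They have no pass/fail rule, so their value lies in the estimate and its interval. Table 5 lists the PD3 GMCs among the interim endpoints meant to inform decisions on future studies.

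**Working it through.** **Inputs from the documents.** 350 subjects per group and 85% evaluable (Section 8.9.1); three arms at 1:1:1; 95% t-interval with pooled variance (Section 8.6.1).

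**Inputs assumed, because the documents give none.** SD of ln IgG 0.8 to 1.2; share of ln-IgG variance explained by country (R²) 0 to 0.20; number of countries (C) 3 to 6.

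**Step 1: reproduce the plan's figure.** 350 x 0.85 = 297.5, which matches the stated ~298 per group. It is the only stated figure that drives GMC precision; no GMC standard deviation, interval width or power is given.

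**Step 2: planned half-width on the ln scale.**
h0 = t(0.975; 891) x SD x sqrt(2/298), with 891 = 3 x 298 - 3.
- SD 0.8: 0.1286, so the ratio is multiplied and divided by 1.137
- SD 1.0: 0.1608, factor 1.174
- SD 1.2: 0.1929, factor 1.213

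**Step 3: half-width with country in the model.**
h1 = t(0.975; 891 - (C - 1)) x SD x sqrt(1 - R²) x sqrt(2/298) x sqrt(1 + (C - 1)/(891 - C)).
The last factor allows for chance imbalance of country between arms. SD cancels in h1/h0.

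Worked line, R² = 0.05 and C = 3: sqrt(0.95) = 0.9747; sqrt(1 + 2/888) = 1.0011; product 0.9758, so the interval is 2.4% narrower. Equivalent sample size: 298/0.9758² = 313 per group.

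| R² (assumed) | Width change, 3 countries | Width change, 6 countries | Equivalent evaluable n per group (3 / 6 countries) |
|---|---|---|---|
| 0 | +0.11% | +0.28% | 297 / 296 |
| 0.02 | -0.89% | -0.73% | 303 / 302 |
| 0.05 | -2.42% | -2.26% | 313 / 312 |
| 0.10 | -5.02% | -4.86% | 330 / 329 |
| 0.20 | -10.46% | -10.30% | 372 / 370 |

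At SD 1.0 the interval factor goes from 1.174 as planned to 1.170 (R² 0.05), 1.165 (R² 0.10) or 1.155 (R² 0.20).

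**Step 4: is chance country imbalance a further harm?** The planned variance of the ln ratio is SD² x 2/298. It splits into a country part, R² x SD² x 2/298, and a residual part, (1 - R²) x SD² x 2/298. At R² = 0.10 and SD 1.0 the country part has a standard deviation of sqrt(0.10 x 2/298) = 0.026, within a total of sqrt(2/298) = 0.082. The planned interval already contains it. Removing it is the same gain as in Step 3, not a second one.

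**Step 5: what does not move.** The only formal test is non-inferiority of response rates by the Miettinen and Nurminen method with margin -0.15. It does not use the GMC model, so the stated power of more than 90% is unaffected.

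**The case against.** The strongest reply is that nothing is wrong. Randomisation is central and unstratified, so the model omits no design factor. The ratio is unbiased and its interval valid, and no decision rule depends on it. Covariate adjustment is then a matter of preference. The facts in this reply stand, and they keep the point minor.

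Four further objections hold in whole or part:
- **The gain is conditional.** Section 8.10 looks for possible country differences; it does not report any. Sections 4.1.4 and 7.1.1.8.2 say that schedules follow local guidance. They do not say that the vaccines given will differ, or that any difference affects pneumococcal IgG. A reader might infer that precision is certainly being lost, but the documents support only that it may be.
- **Age at dose 1.** A reader might also want age in days, which ranges from 42 to 90 at entry. No section supports it as prognostic, and later doses are tied to their own age windows. It is at most optional.
- **Consistency of tables.** Section 8.6.1 reports within-group GMCs as exponentiated raw log means. The planned ratio is their quotient; an adjusted ratio in general is not. This is a real drawback, met by printing both.
- **The supplemental SAP.** Sections 8.0 and 8.9.1 refer to one that is not available here. It could add an adjusted analysis, though Section 8.6.1 itself is explicit about the model.

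**Conclusion.** The point holds as a low-cost improvement with a small expected gain. The planned model is sound and may leave precision unused. For R² of 2%, 5% or 10% the intervals narrow by about 1%, 2.5% or 5%; a gain near 10% would need R² near 20%. If country explains nothing, the loss is at most about 0.3%. These figures rest on assumed values of R², which could differ by serotype and visit, and on 3 to 6 countries; the relative change does not depend on the SD.

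Two stronger readings are not supported. One is that the unadjusted ratios are biased or exposed to an uncovered risk from country imbalance; randomisation and Step 4 answer that. The other is that the primary non-inferiority conclusion or its power is affected; it is not.

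**What to change.** In Section 8.6.1 and Table 3, or in the supplemental SAP, which Section 8.0 allows for changes made before unblinding:
- Add country as a covariate in the linear model for log IgG at PD3, pre-dose 4 and PD4, with a stated rule for pooling small countries.
- Report the unadjusted ratio alongside the adjusted one, with a note that only the unadjusted ratio equals the quotient of the tabulated within-group GMCs.
- Fix this before the PD3 interim unblinding, since PD3 GMCs are an interim endpoint.

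If the sponsor prefers to keep the simple model as the main analysis, a pre-specified country-adjusted sensitivity analysis is the minimum version. The cost is SAP wording, the pooling rule and a second set of ratios in the tables. No new data are collected.
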